3.3.7 Management of suspected everolimus toxicity

Table 3-7: Criteria for dose-modification in case of suspected everolimus toxicity and re-initiation of everolimus treatment

Toxicity	Actions

Non-hematological toxicity
 
Grade 2 (except pneumonitis – refer to Table 3-6)
 
Grade 3 (except hyperlipidemia*) (except pneumonitis – refer to Table 3-6)
 
Grade 4
	
If the toxicity is tolerable to the patient, maintain the same dose. If the toxicity is intolerable to patient, interrupt everolimus until recovery to grade ≤1. Then reintroduce everolimus at same dose. If event returns to grade 2, then interrupt everolimus until recovery to grade ≤1. Then reintroduce everolimus at same dose level.
 
Interrupt everolimus until recovery to grade ≤1. Then reintroduce everolimus at same dose level. For pneumonitis consider the use of a short course of corticosteroids.
 
Discontinue everolimus.

Hematological toxicity
 
Grade 2 Thrombocytopenia (platelets <75, ≥ 50x10⁹/L)
 
Grade 3 Thrombocytopenia (platelets <50, ≥ 25 x10⁹/L)
 
Grade 4 Thrombocytopenia (platelets < 25 x10⁹/L)
	
Interrupt everolimus until recovery to grade ≤1 (>75 x10⁹/L). Then reintroduce everolimus at initial dose. If thrombocytopenia again returns to grade 2, interrupt everolimus until recovery to grade ≤1. Then reintroduce everolimus at same dose level.
 
Interrupt everolimus until recovery to grade ≤1 (platelets ≥ 75 x10⁹/L). Then resume everolimus at same dose level. If grade 3 thrombocytopenia recurs, discontinue everolimus.
 
Discontinue everolimus.

Toxicity	Actions
Grade 3 Neutropenia (neutrophils $<1, \geq 0.5 \times 10^9/L$)	Interrupt everolimus until recovery to grade ≤ 1 (neutrophils $\geq 1.5 \times 10^9/L$). Then resume everolimus at the initial dose. If ANC again returns to Grade 3, hold everolimus until the ANC $\geq 1.5 \times 10^9/L$. Then resume everolimus dosing at same dose level. Discontinue patient from study therapy for a third episode of grade 3 neutropenia.
Grade 4 Neutropenia (neutrophils $< 0.5 \times 10^9/L$)	Interrupt everolimus until recovery to grade ≤ 1 (neutrophils $\geq 1.5 \times 10^9/L$). Then resume everolimus at the lower dose level. If grade 3 or grade 4 neutropenia occurs despite this dose reduction, discontinue everolimus.
Grade 3 febrile neutropenia (not life-threatening)	Interrupt everolimus until resolution of fever and neutropenia to grade ≤ 1 . Hold further everolimus until the ANC $\geq 1,500/mm^3$ and fever has resolved. Then resume everolimus at same dose level. If febrile neutropenia recurs, discontinue everolimus.
Grade 4 febrile neutropenia (life-threatening)	Discontinue everolimus.
Any hematological or non-hematological toxicity requiring interruption for ≥ 3 weeks	Discontinue everolimus

*Grade 3 hyperlipidemia (hypercholesterolemia and/or hypertriglyceridemia) should be managed using medical therapies (see Sec. 3.3.4).

Patients whose treatment is interrupted or permanently discontinued due to an adverse event or abnormal laboratory value suspected to be related to everolimus must be followed at least weekly until the adverse event or abnormal laboratory resolves or returns to grade 1. If a patient requires a dose delay of > 21 days from the intended day of the next scheduled dose, then the patient must be discontinued from the study.

3.3.8 Management of sorafenib induced skin toxicity

It is common for patients treated with sorafenib to experience skin toxicity (rash/desquamation, hand/foot reaction, etc.). Guidelines for management are specified in the table below.

Table 3-8: Guidelines for management of sorafenib induced skin toxicity

Skin Toxicity Grade	Occurrence	Suggested Dose Modification
Grade 1: Numbness, dysesthesia, paresthesia, tingling, painless swelling, and erythema or discomfort of the hands or feet which does not disrupt the patient's normal activities.	Any occurrence	Continue treatment with sorafenib and consider topical therapy for symptomatic relief.
Grade 2: Painful erythema and swelling of the hands or feet and/or discomfort affecting the patient's normal activities.	First occurrence	Continue treatment with sorafenib and consider topical therapy for symptomatic relief. If no improvement within 7 days, see below.
	No improvement within 7 days or 2 nd occurrence	Interrupt sorafenib treatment until toxicity resolves to Grade 0-1. When resuming treatment, decrease sorafenib dose by one dose level.
	Third occurrence	Interrupt until resolved to grade 0-1. When resuming treatment, decrease dose by two dose levels (from the starting dose).
Grade 3: Moist desquamation, ulceration, blistering or severe pain of the hands or feet, or severe discomfort that causes the patient to be unable to work or perform activities.	First occurrence	Interrupt sorafenib treatment until toxicity resolves to Grade 0-1. When resuming treatment, decrease sorafenib by one dose level.
	Second occurrence	Interrupt until resolved to grade 0-1. When resuming treatment, decrease dose by two dose levels (from the starting dose).
	Third occurrence	Discontinue sorafenib treatment.

Table 3-9: Dose Modifications for Sorafenib-Associated Toxicity¹

Toxicity	Grade 1	Grade 2	Grade 3*	Grade 4*
Non-hematologic	Continue at the same dose level.	Continue at the same dose level.	Withhold dose until toxicity is < 1. When resuming treatment reduce dose by one dose level.	Discontinue treatment.
Hematologic	Continue at the same dose level.	Continue at the same dose level.	Withhold dose until toxicity is grade <2. When resuming treatment reduce dose by one dose level.	Withhold dose until toxicity is grade <2. When resuming treatment reduce dose by two dose levels.

¹ See separate suggestions for dose modification due to hand-foot skin reactions.

*Patients who develop grade 3 fever/chills, grade 3 elevation of hepatic transaminases with ALT and AST <10X ULN, grade 3 hyperlipidemia or hyperamylasemia without clinical or other evidence of pancreatitis, grade 3 leukopenia, or grade 3/grade 4 lymphopenia may continue study treatment without interruption at the discretion of the investigator.

3.3.9 Hypertension: Dose Modifications of Sorafenib for Hypertension

Hypertension is a known and potentially serious adverse event associated with sorafenib treatment. Patients will have their blood pressure monitored and recorded weekly during the Cycle 1 and then every cycle of the entire treatment period, either at the doctor's office or by using any calibrated electronic device (such as those found at a local drug store or pharmacy). Patients will have a Blood Pressure Diary on which to record the measurements, which will be kept with research chart. If the patient's blood pressure is elevated at any time (>140/100), even outside clinic visits, they should contact their treating physician.

Table 3-10: Dose modifications for Sorafenib-associated hypertension

Grade (CTCAE v 4.0)	Antihypertensive Therapy	Blood Pressure Monitoring	Sorafenib Dose
Grade 1	None	Routine	No change
Grade 2 (asymptomatic)	Initiate monotherapy (suggest dihydropyridine calcium-channel blocker)	Increase frequency and monitor (by health professional) every 2 days until stabilized	No change
Grade 2 (symptomatic/persistent) OR Diastolic BP > 110 mm Hg OR Grade 3	Add agent(s): Ca ⁺⁺ channel blocker (if not already used), K ⁺ channel opener (angiotensin blockers), beta-blocker, thiazide diuretic	Increase frequency and monitor (by health professional) every 2 days until stabilized; continue qod monitoring to stabilization after dosing restarted.	Hold* Sorafenib until symptoms resolve and diastolic BP < 100 mm/Hg. Resume treatment at 1 dose level lower**
Grade 4			Off protocol therapy

* Patients requiring a delay of > 28 days should go off protocol therapy unless, in the treating physician's opinion, the patient may benefit from continued treatment.
 
** Patients requiring >2 dose reductions should go off protocol therapy.
			

CTCAE v 4.0 definitions
 
Grade 1: asymptomatic, transient (<24 hrs) increase by > 20 mmHg (diastolic) or > 150/100 if previously WNL; intervention not indicated
 
Grade 2: recurrent or persistent (>24 hrs) or symptomatic increase by >20 mmHg (diastolic) or to >150/100 if previously WNL; monotherapy may be indicated.
 
Grade 3: requiring more than one drug or more intensive therapy than previously
 
Grade 4: life threatening (e.g., hypertensive crisis)
			

For treatment or dose modification related questions, please contact the Study Chair or the BTTC Coordinating Center's Research Nurse.

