3.2 PHASE II STUDY DESIGN

3.2.1 Drug Administration

All patients treated on the phase II cohorts will receive a combination of sorafenib (7 days on, 7 days off) and everolimus daily over a 28-day cycle, as follows:

Sorafenib 400 mg BID PO (days 1-7 and days 15-21)

Everolimus 5 mg PO daily (days 1-28)

There is not a defined set of maximum number of cycles that a patient may have. Patients may continue with protocol therapy until criteria for “Off Treatment” is met. See Section **3.7.1**.

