10.2.10.1.1 Agents that may Increase Everolimus Blood Concentrations

CYP3A4 Inhibitors and Pgp Inhibitors: In healthy subjects, compared to everolimus treatment alone there were significant increases in everolimus exposure when everolimus was co-administered with:

- ketoconazole (a strong CYP3A4 inhibitor and a Pgp inhibitor) - Cmax and AUC increased by 3.9- and 15.0-fold, respectively.
- erythromycin (a moderate CYP3A4 inhibitor and a Pgp inhibitor) - Cmax and AUC increased by 2.0- and 4.4-fold, respectively.
- verapamil (a moderate CYP3A4 inhibitor and a Pgp inhibitor) - Cmax and AUC increased by 2.3- and 3.5-fold, respectively.

Concomitant strong or moderate inhibitors of CYP3A4 and Pgp inhibitors should not be used.

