10.2.10.1.2 Agents that may Decrease Everolimus Blood Concentrations

CYP3A4 Inducers: In healthy subjects, co-administration of everolimus with rifampin, a strong inducer of CYP3A4, decreased everolimus AUC and Cmax by 64% and 58% respectively, compared to everolimus treatment alone. Consider a dose increase of everolimus when co-administered with strong inducers of CYP3A4 or Pgp if alternative treatment cannot be administered.

Agents whose Plasma Concentrations may be Altered by Everolimus Studies in healthy subjects indicate that there are no clinically significant pharmacokinetic interactions between everolimus and the HMG-CoA reductase inhibitors atorvastatin (a CYP3A4 substrate) and pravastatin (a non-CYP3A4 substrate) and population pharmacokinetic analyses also detected no influence of simvastatin (a CYP3A4 substrate) on the clearance of everolimus.

Patients will be instructed not to take any additional medications (including over-the-counter products) during the course of the study without prior consultation with the investigator. At each visit, the investigator will ask the patient about any new medications he/she is or has taken after the start of the study drug.

All Concomitant medications/Significant non-drug therapies taken \leq 30 days prior to start and after start of study drug, including physical therapy and blood transfusions, should be recorded.

- Growth factors (e.g. G-CSF, GM-CSF, erythropoietin, platelets growth factors etc.) are not to be administered prophylactically but may be prescribed by the investigator for rescue from severe hematologic events, if this is thought to be appropriate.
- Concurrent administration of everolimus and strong CYP3A4 inhibitors (such as ketoconazole, itraconazole, ritonavir) and inducers (such as rifampin, rifabutin) should be

avoided. Provided there is no alternative treatment available, patients should be closely monitored for potential toxicities.

- Concurrent administration of everolimus and moderate CYP3A4 inhibitors (such as erythromycin, fluconazole, calcium channel blockers, benzodiazepines) and moderate CYP3A4 inducers (e.g. carbamazepine, phenobarbital) should also be avoided if possible, or used subject to caution (e.g. increased frequency of safety monitoring, temporary interruption of everolimus).
- Competitive inhibition could occur when everolimus is combined with drugs which are also CYP3A4 substrates. Therefore caution should be exercised in such cases.

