10.2.12.7 CYP3A4 Interactions

Due to significant increases in exposure of everolimus, co-administration with strong or moderate inhibitors of CYP3A4 (e.g., ketoconazole, itraconazole, clarithromycin, atazanavir, nefazodone, saquinavir, telithromycin, ritonavir, amprenavir, indinavir, nelfinavir, delavirdine, fosamprenavir, voriconazole, aprepitant, erythromycin, fluconazole, grapefruit juice, verapamil or diltazem) or P-glycoprotein (PgP) should be avoided.

Everolimus is a substrate of CYP3A4, and also a substrate and moderate inhibitor of the multidrug efflux pump PgP. In vitro, everolimus is a competitive inhibitor of CYP3A4 and a mixed inhibitor of CYP2D6.

10.2.12.7.1 Agents that may Increase Everolimus Blood Concentrations CYP3A4 Inhibitors and PgP Inhibitors:

In healthy subjects, compared to everolimus treatment alone there were significant increases in everolimus exposure when everolimus was coadministered with:

- ketoconazole (a strong CYP3A4 inhibitor and a PgP inhibitor) - C_{max} and AUC increased by 3.9- and 15.0-fold, respectively.
- erythromycin (a moderate CYP3A4 inhibitor and a PgP inhibitor) - C_{max} and AUC increased by 2.0- and 4.4-fold, respectively.
- verapamil (a moderate CYP3A4 inhibitor and a PgP inhibitor) - C_{max} and AUC increased by 2.3- and 3.5-fold, respectively.

Concomitant strong or moderate inhibitors of CYP3A4 and P-gP inhibitors should not be used.

10.2.12.7.2 Agents that may Decrease Everolimus Blood Concentrations CYP3A4 Inducers:

In healthy subjects, co-administration of everolimus with rifampin, a strong inducer of CYP3A4, decreased everolimus AUC and C_{max} by 64% and 58% respectively, compared to everolimus treatment alone. Consider a dose increase of everolimus when co-administered with strong inducers of CYP3A4 or P-gP if alternative treatment cannot be administered.

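### Table 3-10's row for symptomatic Grade 2 or Grade 3 hypertension does not exclude verapamil or diltiazem, and the everolimus sections disagree on how firmly to restrict them

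*Combined protocol and SAP*

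**What the plan says.** Table 3-10 in section 3.3.9 has four data rows. Grade 1 calls for no drug. Asymptomatic Grade 2 calls for monotherapy and suggests a dihydropyridine. The third row (symptomatic or persistent Grade 2, diastolic pressure above 110 mm Hg, or Grade 3) says to add agents and lists a calcium "channel blocker (if not already used") with angiotensin blockers, a beta-blocker and a thiazide. Grade 4 ends protocol therapy.

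The third row's dosing instruction concerns one drug: "Hold* Sorafenib until symptoms resolve" and diastolic pressure is below 100. It says nothing about everolimus, which section 3.2.1 schedules as "Everolimus 5 mg PO daily (days 1-28").

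The restrictions are in section 10.2:

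- 10.2.10.1.1 reports for everolimus: "verapamil (a moderate CYP3A4 inhibitor and a Pgp inhibitor) - Cmax and AUC increased by 2.3- and 3.5-fold, respectively". It concludes: "Concomitant strong or moderate inhibitors of CYP3A4 and Pgp inhibitors should not be used".
- 10.2.12.7 ends its list of inhibitors with "grapefruit juice, verapamil or diltazem) or P-glycoprotein (PgP) should be avoided", and 10.2.12.7.1 adds: "Concomitant strong or moderate inhibitors of CYP3A4 and P-gP inhibitors should not be used".
- Among the bullets of 10.2.10.1.2, one names "moderate CYP3A4 inhibitors (such as erythromycin, fluconazole, calcium channel blockers, benzodiazepines") and says to avoid them where possible or otherwise use them cautiously, for example with closer monitoring or a pause in everolimus. A later bullet applies the same softer rule to P-glycoprotein inhibitors.

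**The concern.** Table 3-10 is the page an investigator would consult when blood pressure rises on sorafenib, and section 10.1.12 lists hypertension as a very common reaction (10% or more). The third row names a drug class that includes two agents the protocol elsewhere says to avoid with everolimus, without excluding them or giving a cross-reference. An investigator who then looks up the interaction text can reach either a prohibition or a caution, depending on the section.

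What is at stake is patient safety: raised everolimus exposure in someone who is already being managed for toxicity, while only sorafenib is held.

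**Working it through.** The plan gives no figure of its own on this point, so the check sets the texts side by side and then sizes the interaction.

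**1. Which row is open.** The dihydropyridine wording is in the second row, is only a suggestion, and applies to asymptomatic Grade 2. The third row has no subclass wording. A patient who first presents with Grade 3 or a diastolic pressure above 110, or who began on another drug class, reaches the third row with no calcium-channel blocker on board.

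**2. Whether verapamil and diltiazem fall within it.** Table 13-1 (Appendix 13.3) lists both under calcium channel blockers and again under CYP3A inhibitors. The row's wording therefore does not exclude them.

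**3. The rules that apply to verapamil,** which 10.2.10.1.1 classes as both a moderate CYP3A4 inhibitor and a Pgp inhibitor:

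| Section | Basis | Strength |
|---|---|---|
| 10.2.10.1.1 | moderate CYP3A4 inhibitor; Pgp inhibitor | not to be used |
| 10.2.12.7.1 | same | not to be used |
| 10.2.12.7 | named | avoid |
| 10.2.10.1.2, CYP3A4 bullet | calcium-channel blocker | avoid if possible, else caution |
| 10.2.10.1.2, P-glycoprotein bullet | Pgp inhibitor | avoid if possible, else caution |

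All five point towards avoidance, but the first two bar the drug and the last two leave an exception. Diltiazem is named in 10.2.12.7 and falls under the calcium-channel-blocker caution in 10.2.10.1.2.

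**4. Whether another section settles it.** Section 4.0 has no general CYP3A4-inhibitor rule, and 4.1.6 leaves necessary therapies to the investigator. Exclusion 2.1.4.16 concerns inducers. Section 10.2.10.1.2 sends the reader to Table 3-3 for examples, but that is the hepatitis B table; the inhibitor list is in Table 13-1.

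**5. Size.** Inputs: everolimus 5 mg daily (3.2.1); verapamil AUC ratio 3.5 in healthy subjects (10.2.10.1.1); AUC proportional to dose from 5 to 70 mg (10.2.13, in a passage on single doses).

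- Verapamil: 5 mg × 3.5 = 17.5 mg AUC-equivalent. The highest everolimus dose in Table 3-1 is 10 mg, and 17.5 / 10 = 1.75.
- Diltiazem: the documents give no everolimus figure. If it acts as a moderate inhibitor as defined in the notes to Table 13-1 (2- to 5-fold AUC), the range is 5 × 2 = 10 mg to 5 × 5 = 25 mg. This is an assumption. Table 13-1 does not mark diltiazem as strong, and the measured ratios for verapamil (3.5) and erythromycin (4.4) fall inside the moderate range.

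The sorafenib reductions in Table 3-2 would not offset this, because everolimus stays at 5 mg at every level.

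**The case against.** The strongest reply is that the restriction already exists. Section 10.2.12.7 names both drugs, Table 13-1 lists both as inhibitors, and two sections bar their class. A class name in a sorafenib hypertension table does not override named-drug advice in the everolimus sections. The third row also offers three other drug classes, so avoidance will usually be possible, and section 3.3.9 sends dosing questions to the Study Chair or the research nurse. The phrase about a blocker not yet in use follows directly after the dihydropyridine suggestion, so a natural reading is to add that same type of drug.

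Most of this stands, and it keeps the point minor. A reader might infer that the protocol directs, or plainly permits, verapamil or diltiazem. The documents do not support that: neither drug is named in Table 3-10, and every interaction section leans towards avoiding them. Nor is the asymptomatic Grade 2 row at fault, since its suggestion points away from both drugs.

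What the reply does not remove is the missing exclusion in the third row and the difference in strength between 10.2.10.1.1 and 10.2.10.1.2. The natural reading of the row is likely but not stated, and the softer bullets can be read as supporting an exception.

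**Conclusion.** The point holds as a minor safety inconsistency. The third data row of Table 3-10 does not exclude two drugs that 10.2.12.7 says to avoid during everolimus treatment, and the protocol applies rules of different strength to them.

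The 17.5 mg figure for verapamil is an illustration. It assumes that the healthy-subject ratio carries over to patients and that single-dose proportionality holds under daily dosing. The diltiazem range rests on an assumed inhibitor class. The documents do not say how many patients would receive either drug.

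Reach is limited. Section 2.4 marks every cohort except Group B as closed, and section 9.4 says that subjects at non-NCI sites were off treatment by Amendment C. Table 3-7 also interrupts or stops everolimus for many toxicities.

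A reader might go on to infer that higher exposure would disturb the progression-free survival endpoints or trigger the Bayesian toxicity stopping rule in section 7.2. With no usage rate and no exposure-toxicity relation in the documents, neither inference can be supported, and neither is made here.

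**What to change.** In the third data row of Table 3-10, replace the calcium-channel-blocker entry with: *dihydropyridine calcium-channel blocker only (not verapamil or diltiazem; see 10.2.10.1 and 10.2.12.7)*.

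In 10.2.10.1.2, leave the existing bullets as they are, including the caution on calcium-channel blockers as a class, and add a separate bullet: *Verapamil and diltiazem should not be used with everolimus; this overrides the caution wording in the CYP3A4 and P-glycoprotein bullets.* The two names should not go into the existing caution bullet, which would then allow and forbid the same drugs.

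This is a cheap improvement: two wording changes, with no change to design, sample size or endpoints. The downside is a slightly narrower choice of antihypertensive. The change does not settle the same difference in strength for other inhibitors, such as erythromycin, which also falls under both rules.

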3.4 QUESTIONNAIRES

The MDASI-BT will be utilized for this portion of the study. Full instruments are provided in the Appendix 13.4. In addition, information regarding demographics and treatment history will be collected as part of the larger study and used in this analysis.

The MDASI-BT consists of 23 symptoms rated on an 11-point scale (0 to 10) to indicate the presence and severity of the symptom, with 0 being “not present” and 10 being “as bad as you can imagine.” Each symptom is rated at its worst in the last 24 hours. Symptoms included on the instrument include those commonly associated with cancer therapies, those associated with increased intracranial pressure, and those related to focal deficits. The questionnaire also includes ratings of how much symptoms interfered with different aspects of a patient’s life in the last 24 hours. These interference items include: general activity, mood, work (includes both work outside the home and housework), relations with other people, walking, and enjoyment of life. The interference items are also measured on 0 - 10 scales. The average time to complete these instruments is 5 minutes. The MDASI-BT has been translated into 18 languages ([24](#), [25](#)).

3.5 STUDY CALENDAR

STUDIES TO BE OBTAINED	PRE TREATMENT	DURING TREATMENT	OFF TREATMENT
Consent & HIPAA Authorization	X		
History	X ¹		
Physical exam (including vital signs) and Neurologic Examination	X ¹	X ⁵	
Karnofsky Performance Status	X ¹	X ⁵	
Blood Pressure	X ¹	X ¹⁴ , X ⁵	
CBC, with differential, platelets	X ¹	X ⁴ , X ¹⁵	
PT, PTT	X ¹		
Serum creatinine, phosphate, lipase, amylase, bilirubin, SGOT, fasting serum glucose, fasting lipid panel	X ¹	X ⁵ , X ¹⁵	
HBV-DNA, HbsAg, HBsAb, HBcAb, HCV-RNA-PCR	X ¹		
MRI or CT (brain) (X ⁵ (times 2) or X ⁵ (times 4) whichever is applicable per section 3.6.1.2)	X ¹	X ⁵ (times 2) or X ⁵ (times 4) then X ⁶ , X ¹⁶	
MDASI Symptom Assessment X ⁵ (times 2) or X ⁵ (times 4) whichever is applicable per sections 3.6.1.2 and 3.6.1.5	X ¹⁰	X ⁵ (times 2) or X ⁵ (times 4) then X ⁶	
ECG	X ³		
Chest X-ray or chest CT	X ³		

STUDIES TO BE OBTAINED	PRE TREATMENT	DURING TREATMENT	OFF TREATMENT
Urinalysis with microanalysis	X ¹		
Serum pregnancy test (β-HCG)	X ²		
UPC ratio	X ¹²	X ¹²	
Urine Dipstick/urinalysis	X ¹	X ⁵ , X ¹⁵	
HBV-DNA, HCV-RNA-PCR		X ⁹	
Prophylactic antiviral agent (i.e. Lamivudine)	X ¹¹	X ¹¹	X ¹¹
Documentation of tumor diagnosis	X		
Information on drug doses, concomitant medications and doses, (baseline and treatment related) toxicity monitoring	X	X ⁵	
Measurable lesions with measurements-tumor response (X ⁵ or X ⁶ , whichever is applicable per section 3.6.1.2)	X	X ⁵ , X ⁶	
Follow up for survival by phone or clinic visit on patients who discontinue treatment due to progression			X ⁷
Follow up for survival by phone or clinic visit, for those who come off treatment other than progression should be followed until progression or institution of new anti- tumor therapy			X ⁷
Adverse Events Notation	X	X ¹³	

X¹ To be performed within 14 days of registration

X² To be performed within 14 days prior to starting study treatment

X³ To be performed within 30 days prior to starting study treatment

X⁴ To be performed every 2 weeks during treatment

X⁵ To be performed every 4 weeks during treatment (prior to each cycle);

X⁶ To be performed every 2 months during treatment (every other month)

X⁷ To be performed every 3 months

X⁸ To be performed weekly for Phase I Cycle 1

X⁹ To be performed on Cycle 1 Day 1 and Day 1 of all subsequent cycles. Applicable to patients that are on antiviral prophylaxis treatment or positive HBV antibodies, and patients with positive

HCV RNA- PCR results at screening and/or a history of past infection (even if treated or considered cured).

X¹⁰ To be performed within 14 days (+3 working days) after enrollment on the clinical trial.

X¹¹ All patients with positive HBV-DNA or HBsAg should be treated prophylactically with antiviral agent to be given 1 -2 weeks prior to study drugs, and should continue throughout the entire study period, to

last until at least 4 weeks after the last dose of everolimus.

X¹² If urinalysis has > 2+ protein present, then UPC will be obtained

X¹³ To be performed at the end of each cycle

X¹⁴ To be performed weekly during Cycle 1

X¹⁵ Lab work (blood draws/urine) has a window of +/- 3 days of the cycle

X¹⁶ MRI/CT imaging has a window of within 7 days of new cycle

